5.2.2.3 Responsibilities for SAE reporting

Upon inclusion into a trial, the patient's condition is assessed (e.g. documentation of history / concomitant diagnoses and diseases), and relevant changes from baseline are noted subsequently.

All adverse events, serious and non-serious, occurring during the course of the clinical trial (i.e., from signing the informed consent onwards through through 28 days following cessation of treatment) will be collected, documented by the investigator.

The investigator shall report all SAEs and non-serious AEs which are relevant to a reported SAE by fax using BI IIS SAE form to BI Unique Entry Point as detailed below in accordance with the following timelines:

- within five (5) calendar days upon receipt of initial and follow-up SAEs containing at least one fatal or immediately life-threatening event;
- within ten (10) calendar days upon receipt of any other initial and follow-up SAEs.

Boehringer Ingelheim Pharmaceuticals, Inc

[name]
[name]
[contact]
E-mail: [contact]

For each adverse event, the investigator will provide the onset date, end date, intensity, treatment required, outcome, seriousness, and action taken with the investigational drug. The investigator will determine the relationship and expectedness with the investigational drug to all AEs as defined in the listed adverse event section of Boehringer Ingelheim's (BI's) Investigator Brochure for the Product.

The investigator does not need to actively monitor patients for adverse events once the clinical trial has ended. However, if the investigator becomes aware of an SAE(s) that occurred after the patient has completed the clinical trial (including any protocol specified follow-up period), it should be reported to BI if investigator considers it as relevant to the BI study drug.

5.2.3 Assessment of safety laboratory parameters

Safety laboratory samples will be analyzed *at the individual participating site laboratory*. Safety laboratory examinations will include hematology, biochemistry and urine examinations. Table 5.2.3: 1 presents the laboratory tests to be performed.

Table 5.2.3:1 Clinical Laboratory Tests

Category	Parameters
Hematology	haemoglobin, haematocrit, platelet count, blood cell count (WBC)
Chemistry	
Electrolytes	sodium, potassium, calcium, magnesium,
Liver function tests	alkaline phosphatase, aspartate aminotransferase (AST), alanine aminotransferase (ALT), γ -glutamyltransferase (GGT), total bilirubin
Renal function parameters	Blood urea/blood urea nitrogen (BUN), creatinine; Creatinine clearance (see Section 10.2).
Other	glucose, albumin.

The investigator should complete additional evaluations of laboratory tests as clinically indicated. Any abnormal findings from these investigations need to be reported as an Adverse Event.

5.2.4 Assessment of other safety parameters**5.2.4.1 Physical examination, vital signs, height and weight**

A full physical exam will include cardiopulmonary examination, examination of the regional lymph nodes, and examination of the abdomen and an assessment of the mental and neurological status. Additional symptoms which have not been reported during a previous examination will be clarified. Wherever possible the same investigator should perform this examination.

A complete physical examination will be done at Screening, Day 1 of every treatment cycle, and at the End-of-Treatment visit. A symptom-directed examination is to be performed on all other visits.

5.2.4.2 Vital signs

Blood pressure [systolic and diastolic], pulse rate, temperature, height (cm) and body weight (kg) and ECOG performance status (see section 10.3) will be assessed at the times specified in the flow chart.

5.3 Other**5.3.1 Demographics and history**

Demographics (sex, birth date), information on smoking and alcohol history, and baseline conditions will be collected during the screening visit.

The date of first histological diagnosis (month and year may be sufficient), type of tumour histology, biomarker-status (if appropriate), and initial levels of tumour marker (if appropriate) will be reported in the (e)CRF. The number and locations of metastatic sites (if appropriate) as well as the stage according to the tumour, (lymph) node, metastasis (TNM) classification will be provided as obtained at diagnosis and at the inclusion into the trial. Previous surgery and radiotherapy will be reported.

Previously administered chemo- or radiotherapy will be reported including start and end dates (month and year may be sufficient), the therapy protocol with the number of courses (chemotherapy), total radiation dose and radiation field (radiotherapy) and the best response obtained (complete response, partial response, stable disease, progressive disease, unknown).

5.4 Appropriateness of measurements

The RECIST criteria 1.1 (section 10.4) (100) to be used for evaluation of tumour response are well established and scientifically accepted. The US NCI CTCAE criteria Version 3.0 (or 4.0) are used in the assessment of adverse events in cancer patients.

6. INVESTIGATIONAL PLAN**6.1 Visit schedule****6.1.1 Treatment period**

In case a patient misses the scheduled study visit but reports to the investigative site before the next scheduled study visit, the missed visit will be performed. The current date and reason for the delayed visit will be noted in the source documentation. All subsequent study

visits should take place at the start of the next treatment cycle per the flow chart. In the event of any study drug interruption or delay of treatment, the tumour assessment scheduled will not be changed.

6.1.2 End-of-Treatment and Follow-up period.

In the case study medication is permanently discontinued due to reasons other than disease progression, withdrawal of consent, or ability to access Gilotrif outside of the protocol, patients will be followed up for tumour response until disease progression. Follow up will be every *1 month* to document the date of disease progression. Tumor assessment data collection will be discontinued upon progression of the tumour and/or the patient commences other anti-cancer treatment. The investigator will maintain contact every *3 months*, whether by telephone or out-patient attendance, with the patient or the patient's family.

6.1.3 Observational Period

Vital status contacts will occur every 4 weeks, as specified in the flow chart.

Endpoint Sweep

Before each pre-specified data analysis, the site will contact patients and/or their health care providers to collect patients' vital status to ensure that the most up-to-date vital status information is presented in the analysis. Death information from public sources, e.g. death registry, obituary listing, etc. can also be used when it available and verifiable. This approach is referred to as an endpoint sweep in the literature.

6.2 Details of study procedures at selected visits

6.2.1 Screening period

Patients, who have confirmed diagnosis of PSCC and availability of archived biopsy specimen, will undergo screening in 2 visits. First visit will be 30 days before day 1 of cycle 1 and second visit will be 14 days prior to day 1 of cycle 1.

On first visit, the patients will be seen in outpatient clinic and a detailed history will be taken about details pertaining to their course of disease which will include smoking history, demographic information like age, and ethnicity as well as assessment of concomitant medication and adverse events seen in the past if any. Their heights will be recorded and the patients will then undergo CT scan of chest, abdomen and pelvis and details about lesions and spread of cancer will be noted. If the patient has complaints of bone pain in the past, they will also undergo an additional bone scan to determine spread of disease to the bone. All the imaging details will be recorded as baseline records which will be compared to determine disease progression in follow up scans.

At the second visit for screening in outpatient clinic, the patients will have their blood pressure and weight recorded. They will then undergo detailed physical examination by the study doctor. About 10 ml of blood will be withdrawn in laboratory for routine complete blood count with differential count along with complete metabolic panel.

The study doctor will calculate ECOG performance status from the information collected at screening visit.

All details collected in the 2 visits will be first recorded in patient case files and then transferred to CRF provided by the sponsor.

For those patients who will be determined eligible for the study, archived tumor biopsy specimen will be obtained and reviewed by central laboratory. This specimen will be used to prepare 20 Formalin Fixed Paraffin Embedded slides. Of these, 15 slides will have sections of 10 μM thickness while 5 slides will have sections of 5 μM thickness. The slides with 10 μM thickness will be sent to [name] laboratory situated in UAB Department of Radiation Oncology for gene expression studies using nanostring technology. Immunohistochemistry studies and HPV DNA analysis will be conducted on 5 μM thick sections.

6.2.2 Treatment period(s)

Patients who are eligible for the study, will then start treatment cycles with Gilotrif 40 mg per day dosage. Patient taking oral Gilotrif tablets every day for 28 days will have completed one cycle. On day 1 of each cycle patient will visit clinic.

History will be taken on course of disease since screening and during the cycle of treatment along with adverse events assessment during treatment cycle; weight and blood pressure will be recorded; detailed physical examination will be conducted; blood will be withdrawn for routine complete and differential blood count as well as complete metabolic profile.

Patients will receive bottle of Gilotrif tablets for entire cycle and instructions will be given about intake of medication and other precautions as mentioned in section 4.1.4.1.

On day 1 of 2nd cycle and on follow-up visits every 8 weeks thereof, patients will undergo CT scan of chest, abdomen and pelvis to document response of disease to the medication. If the patient had undergone baseline Bone scan at screening visit, a repeat bone scan will be conducted along with CT scan.

ECOG performance status will be calculated at each visit to determine if patient is tolerating the treatment well.

Details of assessments done for safety considerations of patients on treatment have been discussed in detail in sections 5.2.3, 5.2.4 and 5.3.

6.2.3 End of study treatment and follow-up period

Once the patient stops taking treatment for any reason (disease progression, adverse events or withdrawal of consent), a repeat CT scan of chest, abdomen and pelvis will be conducted 28 \pm 3 days after the last dose of Gilotrif.

All other assessments will be repeated at this follow-up visit that were conducted on day 1 of each cycle. ECOG performance status will be calculated and recorded.

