Methodology:	
This is a non-randomized 2-center phase II trial (N=29) to evaluate Gilotrif 40 mg po qd for patients with metastatic progressive PSCC following prior chemotherapy.
 
Those progressing within 6 months of prior therapy will be enrolled with the goal of detecting PFS at 6 months after starting Gilotrif in $\geq 20\%$ of patients, while PFS6 in <5% will be considered to be of poor interest. Selecting patients within 6 months of prior therapy will enrich for patients unlikely to attain PFS6 without active therapy. Patients will undergo clinical examination every 4 weeks and radiographic work-up at baseline and then every 8 weeks. Patients will continue therapy until progression or intolerable toxicities. Patients removed from therapy for reasons other than progression will be followed to identify progression or until initiation of other therapy. Twenty archival formalin-fixed paraffin embedded (FFPE) tissue slides per patient will be acquired for potential future analyses including histologic sub-type, HPV status, gene expression (nanostring) and IHC for EGFR, Her2, Her3, Her4.
	
	
The eligible population of patients includes men with pathologically proven locally advanced or metastatic (lymph node or distant metastasis i.e. N+ or M1) PSCC which has received ≥ 1 systemic chemotherapy regimens within the last 6 months with ECOG PS 0-2 & optimal organ function (Hb>8.5, ANC>1500/mm³, Platelet count>100K, Total bilirubin <1.5 of ULN, creatinine clearance >45 ml/minute, ALT and AST<2.5X ULN, for patients with liver involvement ALT and ALT<5X ULN). The disease should be measurable by RECIST 1.1 criteria.
	
	
Gilotrif will be administered orally 40mg daily continuously. Continuous administration of 4 weeks is considered one cycle. Therapy will continue until progression (by RECIST 1.1) or severe toxicities. Patients removed from the trial for toxicities or other reasons will continue to be followed until progression or starting a new agent. Complete Blood Count (CBC) & Comprehensive metabolic panel (CMP) evaluations will be done performed on day 1 every 4 weeks. CT chest, abdomen and pelvis will be performed every 2 cycles (8 weeks). A bone scan will be performed only if bone pain or high alakaline phosphatase.
	
	
Progression of disease will be defined clinically as the first occurrence of any of the following:
 
 1) Progression as defined by RECIST 1.1 criteria 2) Death 	
No. of patients:	29	

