3. DESCRIPTION OF DESIGN AND STUDY POPULATION

3.1 Overall study design and plan

[figure not shown]
This is a non-randomized 2-center phase II trial (overall N=29, evaluable N= 27) to evaluate Gilotrif 40 mg po qd for patients with locally advanced unresectable or metastatic progressive PSCC following prior chemotherapy. UAB is the coordinating institution and the other participating institution is the University of Southern California (USC). Patients will undergo clinical examination every 4 weeks and radiographic work-up at baseline and then every 8 weeks. Patients will continue therapy until progression or intolerable toxicities. Patients removed from therapy for reasons other than progression will be followed to identify progression or until initiation of other therapy. Twenty archival formalin-fixed paraffin embedded (FFPE) tissue slides per patient will be acquired for future analyses including histologic sub-type, IHC for EGFR, Her2, Her3, Her4, gene expression by nanostring for a panel of kinase and cancer associated genes and Human Papilloma Virus status by PCR (polymerase chain reaction) for HPV-DNA.

The eligible population of patients includes men with pathologically proven locally advanced or metastatic (lymph node or distant metastasis i.e. N+ or M1) PSCC which has received ≥ 1 systemic chemotherapy regimens within last 6 months with ECOG PS 0-2 & optimal organ function (Hb>8.5, ANC>1500/mm³, Platelet count>100K, Total bilirubin <1.5 of ULN, creatinine clearance >45ml/min, ALT and AST<2.5X ULN, for patients with liver involvement ALT and ALT<5X ULN). The disease should be measurable by RECIST 1.1 criteria. Gilotrif will be administered orally 40mg daily continuously. Continuous administration of 4 weeks is considered one cycle. Therapy will continue until progression (by RECIST 1.1) or severe toxicities. Patients removed from the trial for toxicities or other reasons will continue to be followed until progression or starting a new agent. Complete Blood Count (CBC) & Comprehensive metabolic panel (CMP) evaluations will be done performed on day 1 every 4 weeks. CT chest, abdomen and pelvis will be performed every 2 cycles (8 weeks). A bone scan will be performed only if bone pain or high alkaline phosphatase are observed. An evaluable patient is defined as any patient who qualifies for the trial and receives at least one dose of study drug.

Progression of disease will be defined clinically as the first occurrence of any of the following:

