3.3.4 Removal of patients from therapy or assessments

Patients will be removed from study when any of the criteria listed below applies. The reason for study removal and the date the patient was removed will be documented in the Case Report Form.

1. Progression of disease as defined by measurable disease using RECIST 1.1
2. Death
3. Intercurrent illness that prevents further administration of treatment
4. Unacceptable adverse event(s)
5. Patient decides to withdraw from the study
6. General or specific changes in the patient's condition render the patient unacceptable for further treatment in the judgment of the investigator.

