7.3.2 Secondary analyses

The secondary endpoints are not formally powered for, but will be examined in the evaluable population. RECIST responses, regression and toxicities will be analyzed as secondary endpoints. Descriptive statistics including frequencies and proportions will be calculated to summarize safety and toxicity outcomes. Specifically, the number of adverse events (AE) and serious adverse events (SAE) will be tabulated and summarized. Point estimates and two-sided, exact binomial (Clopper-Pearson) 95% confidence intervals (CI) will be calculated to estimate the incidence of AEs and SAEs. The precision of these estimates, i.e., width of the confidence interval, will depend on the estimated incidence of each outcome. The table below gives the exact 95% confidence intervals for a range of incidences, assuming 27 evaluable subjects.

Number of subjects experiencing event	Estimated Incidence	95% Exact CI for Incidence		Width of CI
		Lower Limit	Upper Limit	
1	0.037	0.001	0.190	0.189
2	0.074	0.009	0.243	0.234
4	0.148	0.042	0.337	0.295
7	0.259	0.111	0.463	0.352

14	0.519	0.319	0.713	0.394
----	-------	-------	-------	-------

The Kaplan-Meier method will be used to estimate OS rates over time with standard errors estimated using Greenwood's formula. Chi-square or Fisher's exact test will be employed to determine bivariate association of biomarker status with PFS6 and objective response.

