8.1 Study approval, patient information, and informed consent

Prior to patient participation in the study, written informed consent will be obtained from each patient (or the patient's legally accepted representative) according to ICH GCP and to the regulatory and legal requirements of the participating country. Each signature will be personally dated by each signatory and the informed consent and any additional patient-information form retained by the investigator as part of the study records. A signed copy of the informed consent and any additional patient information will be given to each patient or the patient's legally accepted representative.

The patient will be informed that his/her personal study-related data will be used by the Principal Investigator in accordance with the local data protection law. The level of disclosure will also be explained to the patient.

The patient will be informed that his / her medical records may be examined by authorised monitors (CRA) or Clinical Quality Assurance auditors appointed by the Principal Investigator, by appropriate EC members, and by inspectors from regulatory authorities.

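### Section 6.2.3 requires a day-28 CT after any treatment stop, including documented progression, where it serves no tumour endpoint; separately, 6.1.2 drops from tumour follow-up men who can get Gilotrif elsewhere, against 3.1

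*Combined protocol and SAP*

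**What the plan says.** Section 6.2.3 sets one visit after the last dose. "Once the patient stops taking treatment for any reason (disease progression, adverse events or withdrawal of consent), a repeat CT scan" is to be done 28 ± 3 days later, and the day-1 assessments are repeated. Both schedules (the Flow Chart and the Trial Schedule in 3.2) mark CT in the post-treatment column with a plain X under disease assessment. They carry no footnote and do not mention progression or withdrawal of consent.

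Section 6.1.2 covers tumour follow-up after treatment. It applies to men who stop "due to reasons other than disease progression, withdrawal of consent, or ability to access Gilotrif outside of the protocol", and it has a stopping point: "Tumor assessment data collection will be discontinued upon progression of the tumour and/or the patient commences other anti-cancer treatment".

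The synopsis and 3.1 define the follow-up group differently: "Patients removed from therapy for reasons other than progression will be followed to identify progression or until initiation of other therapy". They add: "Patients removed from the trial for toxicities or other reasons will continue to be followed until progression or starting a new agent". Neither makes an exception for men with another source of the drug.

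Section 3.3.4 begins "Patients will be removed from study when any of the criteria listed below applies" and lists progression and the patient's decision to withdraw among those criteria. Section 6.2.4 lists what is collected in the observational period (vital status, drug-related adverse events, anti-cancer therapy), with no imaging.

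**The concern.** There are three separate questions.

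- **Use of the scan after progression.** If nothing in the plan uses it, men with short expected survival undergo a required CT, with radiation and possibly contrast, for no stated purpose. In the second-line paclitaxel trial cited in 1.1.3, median overall survival was 23 weeks.
- **Consent.** A procedure tied to withdrawal of consent should say which consent has been withdrawn: to the drug or to the study.
- **Lost outcomes.** A man who leaves study treatment because he can get the same drug elsewhere may still be progression-free. If 6.1.2 is followed, his six-month status may never be recorded. This is the only one of the three that can touch the primary endpoint.

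**Working it through.** **1. The plan's own figure.** Inputs from 7.1, 7.3.1 and 7.5: 13 men in stage 1, 14 in stage 2, stop at 0 of 13, success at 4 or more of 27, p0 = 5%, p1 = 20%.

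P(success | p) = Σ (x = 1 to 13) C(13,x) p^x (1−p)^(13−x) × P[Bin(14,p) ≥ max(0, 4−x)]

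- p = 0.20: 0.8011, which matches the stated 80.1%.
- p = 0.05: 0.0416, below the one-sided 0.05.
- Stopping at stage 1: 0.95^13 = 0.513 under p0; 0.80^13 = 0.055 under p1.

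No input involves a scan after progression, so no design figure changes.

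**2. Does any tumour endpoint need the post-progression scan?**

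- *PFS6.* Section 3.1 takes the first occurrence of RECIST progression or death as the event. Once progression is documented, a man's status at six months is fixed, whichever side of six months it fell. A later CT cannot change it.
- *Response.* Section 7.3.2 says "RECIST responses, regression and toxicities will be analyzed as secondary endpoints". Regression is not defined, and nothing there asks for imaging after progression.
- *Overall survival.* This needs vital status, not CT.
- *Data collection.* Section 6.1.2 has already stopped tumour data collection at progression. If other anti-cancer therapy has begun by day 28, it has stopped for that reason too.

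So no tumour endpoint in the plan uses the scan.

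**3. Where the scan is useful.** A man who stops for toxicity or clinical decline without documented progression still has an open PFS6 outcome, and the day-28 CT can inform it. The scan should therefore be restricted, not removed.

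**4. Withdrawal of consent.** Section 6.2.3 gives it as a reason for stopping treatment and then orders the CT. Section 6.1.2 excludes the same men from tumour follow-up. Section 8.1 says "written informed consent will be obtained from each patient" before participation; it does not describe what happens on withdrawal. The sections cited here do not separate stopping the drug from leaving the study.

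**5. Access to Gilotrif outside the protocol.** Section 6.1.2 ends tumour follow-up for these men. The synopsis and 3.1 continue it until progression or other therapy. The natural reading of a new agent is a different drug, so continuing Gilotrif from another source should not end follow-up under 3.1. The two rules therefore conflict. The decision thresholds show why one outcome can matter: 4 of 27 is a success and 3 of 27 is not; 1 of 13 continues the trial and 0 of 13 stops it. At either boundary, one progression-free man whose status goes unrecorded could change the decision. Section 7.4 gives no rule for a missing PFS6 status.

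**The case against.** The case for leaving the text alone has several parts.

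- **The two sections describe different activities.** Section 6.2.3 sets a single end-of-treatment visit and 6.1.2 sets monthly follow-up. A site can carry out both. This stands: the scan is an unneeded burden and a poor fit between sections, not an impossible instruction.
- **The schedules are neutral.** A reader might infer that both schedules expressly demand a CT after progression or withdrawal. They do not. They show an unconditional X, and only 6.2.3 names those cases.
- **Withdrawal may mean withdrawal from treatment.** A reader might infer that the protocol authorises a scan against a patient's will. The documents do not support that. The phrase describes why treatment stops, 8.1 puts consent under ICH GCP, and the consent form is not in the available text. What remains is that the wording does not say which consent is meant.
- **The scan might help safety.** Adverse events are reported up to 28 days after the last dose, and 5.2.2.1.5 makes a finding reportable when it is uncertain whether it is due solely to cancer progression. A CT could help with that judgement. But the plan does not give the scan that purpose, both schedules place it under disease assessment, and suspected interstitial lung disease has its own work-up in 4.2.1.3. The fix keeps CT available for adverse events.
- **Outside access is a different issue, and 3.1 does not say whether off-protocol Gilotrif is a new agent.** It is a separate issue and is presented as one. The missing definition is a reason to supply it; it does not reconcile 6.1.2 with 3.1.

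**Conclusion.** The point holds and is minor. After documented RECIST progression, the day-28 CT in 6.2.3 serves no tumour endpoint in the plan. The withdrawal wording needs clarifying. The outside-access exclusion in 6.1.2 conflicts with the synopsis and 3.1 and could lose PFS6 outcomes in men who may still be progression-free.

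A reader might infer that the extra scan biases PFS6 or weakens the design. It does neither: estimates, alpha, power and sample size are unaffected by it. Only the outside-access exclusion can reach the primary endpoint, and the documents do not say how many men it would concern.

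A count of unneeded scans is also tempting, but the documents do not support one. They give no split of reasons for stopping, no post-progression survival on this drug and no attendance rate. They also do not show how many of these men would be scanned anyway before further therapy. The conclusion does not depend on a count. It rests on the text of the sections compared and, for outside access, on reading a new agent as a different drug.

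**What to change.** - **Section 6.2.3, and a footnote to the CT row of both schedules:** limit the day-28 CT to patients without documented RECIST 1.1 progression who have not started other anti-cancer therapy and who still consent to study procedures. Keep the other day-28 safety assessments for all who still consent. Allow a CT whenever an adverse event calls for one.
- **Section 6.1.2:** delete the outside-access exclusion, and state that Gilotrif obtained outside the protocol is not a new agent, so tumour follow-up continues to progression as in 3.1.

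The cost is a few words in two sections and two footnotes. The routine post-progression scan is lost, though it can still be ordered clinically, and a few men will need continued tumour follow-up.
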